## BACKGROUND

Metabolic-associated fatty liver disease (MAFLD) is currently the most common chronic liver disease worldwide, affecting approximately 25-30% of the population, making it a significant public health problem.  It is characterized by the presence of hepatic steatosis in more than 5% of hepatocytes, as demonstrated by biopsy, imaging, or biomarkers, and at least one of the following criteria 1) overweight or obesity, 2) diabetes mellitus, 3) at least two metabolic abnormalities (waist circumference greater than 90 cm in men and 80 cm in women; blood pressure  $\geq 130/85$  mmHg or specific pharmacological treatment; triglycerides  $\geq 150$  mg/dL or specific pharmacological treatment; high-density lipoprotein cholesterol  $< 40$  mg/dL in men and  $< 50$  mg/dL in women or specific pharmacological treatment; fasting glucose  $\geq 100$  mg/dL; insulin resistance index  $\geq 2.5$ ; C-reactive protein  $\geq 2$  mg/dL). 

The increase in the prevalence of MAFLD is favored by sedentary lifestyles and poor dietary habits, such as excessive calorie and saturated fat intake, which coincide with the rise in overweight and obesity. On the other hand, the new definition of MAFLD has moved away from the dichotomy of simple steatosis and steatohepatitis, as it has been demonstrated that fatty liver disease should not be seen as a duality, but as an evolving process in which tissue accumulation of triglycerides can be initially benign with subsequent progression to chronic inflammation and tissue damage (steatohepatitis). The presence of fibrosis is considered a prognostic marker of MAFLD and may be present to varying degrees, with or without inflammation, characterized by the formation of collagen fibers due to the transformation of stellate cells into fibroblast-like cells. 

The hepatic steatosis observed in patients with MAFLD is secondary to excessive synthesis of hepatic triglycerides from fatty acids derived from adipose tissue, de novo lipogenesis, and endocytosis of triglyceride-rich lipoproteins. Furthermore, the excessive triglyceride content in the liver tissue leads to secondary VLDL secretion, which is characteristic of the atherogenic dyslipidemia in patients with MAFLD. These patients also have elevated serum triglycerides, elevated LDL cholesterol, and low HDL cholesterol, explained by the activity of the plasma protein CETP, which

transfers cholesterol from HDL or LDL to triglyceride-rich lipoproteins (TRL). Remnant lipoproteins from lipid metabolism and systemic transport have the ability to passively deposit in arterial walls, triggering atherosclerosis. For this reason, the dyslipidemia present in fatty liver is associated with the risk of cardiovascular diseases and mortality.

In addition to alterations in hepatic triglyceride metabolism, patients with MAFLD experience systemic metabolic dysregulation consistent with components of the metabolic syndrome. The most frequently associated comorbidities, now considered diagnostic criteria, are the presence of diabetes mellitus and obesity.

Currently, there is no approved pharmacological treatment for MAFLD. However, it has been demonstrated that intervention with Mediterranean and hypocaloric dietary styles, with or without exercise regimens, improves intrahepatic fatty acid content and hepatic inflammation, as reflected by a reduction in transaminase levels, when weight loss of 5 to 7% is achieved. Improvement in fibrosis and inflammation can be observed with a 10% weight loss.

Milk thistle (*Silybum marianum*) is a medicinal plant native to North Africa, Southern Europe, and Southern Russia, which contains flavonolignans including silybin, isosilybin, silidianin, and silicristin. It has been used in traditional Chinese medicine for the treatment of liver and biliary diseases. Currently, it has demonstrated antioxidant, anti-inflammatory, and antifibrotic effects in liver diseases, particularly in fatty liver disease. Its therapeutic effects are attributed to the active component of the plant's seeds, known as silymarin. Silibin, the main active component of silymarin, inhibits oxidative stress in the endoplasmic reticulum of hepatocytes and the assembly of the NLRP3 inflammasome through the NAD+/SIRT2 pathway in mice with fatty liver.

On the other hand, alpha-lipoic acid is a cofactor of mitochondrial enzymes that has been considered an antioxidant. Its reduced form, dihydrolipoate, reacts with reactive oxygen species, thereby protecting the cell membrane. Administration of alpha-lipoic acid has been shown to have beneficial effects on adipokine levels and

metabolic disorders such as diabetes and obesity, which are commonly present in patients with MAFLD. It has been demonstrated that the administration of 1200 mg of alpha-lipoic acid in patients with fatty liver disease reduces insulin resistance and serum leptin levels while increasing adiponectin concentration. However, it did not influence liver histology and biochemical markers. 

Therefore, our objective is to demonstrate that the administration of the combination of alpha-lipoic acid and Silybum marianum (LUDLEV®) can improve steatosis in patients with MAFLD when associated with a Mediterranean-style diet, while ensuring a favorable safety profile.

## **RESEARCH QUESTION**

Can supplementation with alpha-lipoic acid and Silybum marianum (LUDLEV®) in combination with a Mediterranean diet improve steatosis and fibrosis in patients with MAFLD?

## **HYPOTHESIS**

The administration of the combination of alpha-lipoic acid and Silybum marianum (LUDLEV®) in combination with a Mediterranean diet reduces the degree of fibrosis and steatosis in patients with MAFLD as assessed by kPa and CAP measurements after 24 weeks of treatment.

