## **OBJECTIVES**

### **Overall objective:**

To evaluate the effects of administering alpha-lipoic acid and Silybum marianum (LUDLEV® 300 mg/46.2 mg) in combination with a Mediterranean diet compared to

placebo plus a Mediterranean diet on fibrosis and steatosis in patients with MAFLD after 24 weeks of treatment.

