### **Specific Objectives:**

- To assess the effects of administering alpha-lipoic acid and Silybum marianum (LUDLEV® 300 mg/46.2 mg) in combination with a Mediterranean diet versus placebo plus a Mediterranean diet on fibrosis and steatosis in patients with MAFLD after 12 weeks of treatment.
- To evaluate changes in fibrosis measured by kPa using FibroScan® elastography after 12 and 24 weeks of administering alpha-lipoic acid and Silybum marianum (LUDLEV® 300 mg/46.2 mg) every 12 hours in combination with a Mediterranean diet, compared to placebo plus a Mediterranean diet in patients with MAFLD.
- To assess changes in the controlled attenuation parameter (CAP) measured by FibroScan® elastography after 12 and 24 weeks of administering alpha-lipoic acid and silybum marianum (LUDLEV® 300 mg/46.2 mg) every 12 hours in combination with a Mediterranean diet, compared to placebo plus a Mediterranean diet in patients with MAFLD.
- To evaluate biochemical improvement after 12 and 24 weeks of administering alpha-lipoic acid and Silybum marianum (LUDLEV® 300 mg/46.2 mg) every 12 hours in combination with a Mediterranean diet, compared to placebo plus a Mediterranean diet in patients with MAFLD.
- To assess weight loss and changes in body composition after 12 and 24 weeks of administering alpha-lipoic acid and Silybum marianum (LUDLEV® 300 mg/46.2 mg) every 12 hours in combination with a Mediterranean diet, compared to a Mediterranean diet alone in patients with MAFLD.

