#### **5. Analysis of the results**

The analysis of the results, elaboration of figures and tables will be carried out with the statistical program IBS SPSS version 22.0. Nominal and ordinal variables will be described with frequencies and percentages; continuous and discrete variables with measures of central tendency and dispersion according to their distribution. The normality of data distribution will be evaluated with the Kolmogorov-Smirnov test, and nonparametric statistics will be used to evaluate intergroup differences between nominal variables. Non-parametric statistics will be used for ordinal variables. A p-value of less than 0.05 will be considered statistically significant.

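### No primary outcome and no both-or-either rule for kPa and CAP at week 24, and a Background aim narrower than the hypothesis, leave the efficacy claim undefined

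*Protocol*

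**What the plan says.** The protocol states its efficacy aim in several places, and they differ.

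- **Background (closing aim):** the product "can improve steatosis in patients with MAFLD when associated with a Mediterranean-style diet", with a favourable safety profile. Fibrosis is not mentioned.
- **Research Question:** steatosis and fibrosis, with no time point.
- **Hypothesis:** the product plus diet "reduces the degree of fibrosis and steatosis in patients with MAFLD as assessed by kPa and CAP measurements after 24 weeks of treatment".
- **Overall objective:** effects "on fibrosis and steatosis in patients with MAFLD after 24 weeks of treatment".
- **Specific Objectives:** effects "on fibrosis and steatosis in patients with MAFLD after 12 weeks of treatment", and then each reading separately at both times: "To evaluate changes in fibrosis measured by kPa using FibroScan® elastography after 12 and 24 weeks" and "To assess changes in the controlled attenuation parameter (CAP) measured by FibroScan® elastography after 12 and 24 weeks". Biochemistry, weight and body composition follow.

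The Sample size calculation uses a further measure, ultrasound-graded steatosis (70% versus 15%). Section 5, Analysis of the results, gives a single decision rule: "A p-value of less than 0.05 will be considered statistically significant". Nowhere is an outcome called primary, and nowhere is it said whether kPa and CAP must both improve.

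**The concern.** CAP and kPa are separate readings of separate features, and one can move without the other. If CAP improves and kPa does not, or the reverse, the protocol cannot say whether its hypothesis was met. The choice would then be made with the results in view.

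Each way of filling the gap has a cost. If one outcome is enough, two chances at p<0.05 raise the false-positive rate above 5%. If both are needed, the error rate is safe, but the trial must succeed on kPa, for which no effect is planned anywhere. The choice of primary outcome belongs in the protocol, so a statistical analysis plan that is not shown does not settle this.

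**Working it through.** **Inputs from the protocol.** Two outcomes, kPa and CAP. Week 24 is fixed in the Hypothesis and Overall objective; week 12 appears only in the Specific Objectives. The threshold is 0.05 per test.

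**Assumptions, because the protocol is silent.** Two-sided tests; correlation between the kPa and CAP test statistics 0 to 0.7; correlation between week 12 and week 24 of 0 to 0.8; no true effect on anything. The protocol states no overall error rate, so there is no figure of its own to reproduce.

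**Step 1: either outcome suffices, independent tests.** The chance of at least one p<0.05 among k tests is 1 − 0.95^k.
- Week 24 only, k = 2: 1 − 0.95² = 1 − 0.9025 = 9.75%.
- Both times, k = 4: 1 − 0.95⁴ = 1 − 0.8145 = 18.55%.

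**Step 2: correlated tests.** The readings come from the same patients and the same device, and the two times are repeated measures, so independence is the upper end. The correlated values below come from 1,000,000 simulated draws of four normal test statistics (two outcomes by two times), counting any |z| > 1.96. The independent values are those of Step 1.

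| Correlation between outcomes | Two tests, week 24 | Four tests, time correlation 0 | Four tests, time correlation 0.8 |
|---|---|---|---|
| 0 | 9.75% | 18.55% | 15.0% |
| 0.3 | 9.5% | 18.2% | 14.6% |
| 0.5 | 9.1% | 17.3% | 13.9% |
| 0.7 | 8.3% | 16.0% | 12.8% |

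The week-24 pair therefore gives about 8% to 10%, and all four tests about 13% to 18.5%. These rates count significance in either direction against a nominal 5%. Counting only results that favour the product, two independent tests give 1 − 0.975² = 4.94% against a nominal 2.5%, so the near-doubling is the same.

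**Step 3: both outcomes required.** A false claim then needs significance on at least one outcome with no true effect, and that single test has a 5% chance at most. With no effect on either outcome, the simulated chance that both are significant in favour of the product at week 24 is 0.06% to 0.8%. There is no inflation. The cost is power. As an illustration only, two independent outcomes with 80% power each succeed together with probability 0.80 × 0.80 = 64%. The protocol gives no effect size or standard deviation for kPa or CAP from which the real figure could be worked out.

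**Step 4: fixed order.** If CAP is tested first at 5%, and kPa at 5% only when CAP is significant, the chance of any false claim over the two tests is at most 5%.

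**The case against.** The strongest reply is that the Hypothesis joins fibrosis and steatosis with an *and*. Read literally, both must improve, and then the false-positive rate is at most 5%. That reading is available and must be reported beside the others. It does not remove the problem: the protocol never states it as a success rule, and under it kPa has no planned power.

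A second reply is that the aims differ less than they may seem to. The Research Question, Hypothesis and Overall objective all name both features, and only the closing aim of the Background is narrower. That is correct, and the inconsistency is confined to that one place.

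A third reply is that testing order and multiplicity adjustment are commonly left to the statistical analysis plan. That is accepted. The absence of an adjustment is not the point here; the unnamed primary outcome and the missing success rule are.

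Two stronger readings are tempting and are not supported:

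- A reader might infer that a result on either outcome at either time proves efficacy, and so quote 18.5%. The Hypothesis and Overall objective both fix 24 weeks, week 12 sits a tier lower, and no passage says that any one result suffices.
- A reader might infer that kPa is an unsuitable outcome because entry requires steatosis but not fibrosis. The protocol assesses kPa as a continuous reading, which can fall within the F0 range, and it gives no expected share of F0 patients. Dilution is possible but cannot be sized.

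**Conclusion.** The point holds in a limited form. The protocol names no primary outcome between week-24 kPa and CAP, gives no both-or-either rule, and states a narrower aim in the Background than elsewhere. If either week-24 outcome may carry the claim, the false-positive rate is about 8% to 10%; if both are required, it is at most 5%, with power for kPa unplanned. The higher range of about 13% to 18.5% applies only if week-12 results are also allowed to count, and it should not be presented as what the protocol implies. All these rates rest on the assumed correlations and on two-sided tests. The ambiguity itself rests on none of them: a mixed result on CAP and kPa has no agreed meaning under the present text.

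**What to change.** Before unblinding:

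1. Align the Background aim with the Hypothesis and Overall objective.
2. State one success rule. Test change in CAP from baseline to week 24, group B versus group A, first at two-sided 5%. Test week-24 kPa at 5% only if CAP is significant.
3. Label all week-12 results and the remaining objectives as supportive.
4. State in the Sample size calculation that the size was based on ultrasound-graded steatosis and not on CAP or kPa. Putting CAP first fits the disease feature used there, but that calculation does not show that the trial is large enough for a change in CAP.

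Requiring both week-24 outcomes would also hold the error rate and would keep fibrosis on an equal footing, but it would need a planned effect and power for kPa.

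The cost is a protocol amendment and an open statement about the basis of the sample size. The downside is that an isolated kPa or week-12 result can no longer carry the efficacy claim.

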## **OBJECTIVES**

### **Overall objective:**

To evaluate the effects of administering alpha-lipoic acid and Silybum marianum (LUDLEV® 300 mg/46.2 mg) in combination with a Mediterranean diet compared to

placebo plus a Mediterranean diet on fibrosis and steatosis in patients with MAFLD after 24 weeks of treatment.

### **Specific Objectives:**

- To assess the effects of administering alpha-lipoic acid and Silybum marianum (LUDLEV® 300 mg/46.2 mg) in combination with a Mediterranean diet versus placebo plus a Mediterranean diet on fibrosis and steatosis in patients with MAFLD after 12 weeks of treatment.
- To evaluate changes in fibrosis measured by kPa using FibroScan® elastography after 12 and 24 weeks of administering alpha-lipoic acid and Silybum marianum (LUDLEV® 300 mg/46.2 mg) every 12 hours in combination with a Mediterranean diet, compared to placebo plus a Mediterranean diet in patients with MAFLD.
- To assess changes in the controlled attenuation parameter (CAP) measured by FibroScan® elastography after 12 and 24 weeks of administering alpha-lipoic acid and silybum marianum (LUDLEV® 300 mg/46.2 mg) every 12 hours in combination with a Mediterranean diet, compared to placebo plus a Mediterranean diet in patients with MAFLD.
- To evaluate biochemical improvement after 12 and 24 weeks of administering alpha-lipoic acid and Silybum marianum (LUDLEV® 300 mg/46.2 mg) every 12 hours in combination with a Mediterranean diet, compared to placebo plus a Mediterranean diet in patients with MAFLD.
- To assess weight loss and changes in body composition after 12 and 24 weeks of administering alpha-lipoic acid and Silybum marianum (LUDLEV® 300 mg/46.2 mg) every 12 hours in combination with a Mediterranean diet, compared to a Mediterranean diet alone in patients with MAFLD.

## **METHODOLOGY**

### **Research Design**

**Study type:** Randomized, controlled, double-blind clinical trial.

### **Population Definition**

Patients regularly attending the outpatient clinic of the Gastroenterology Department of the Instituto de Investigaciones Médico-Biológicas de la Universidad Veracruzana, diagnosed with MAFLD.

### **Inclusion criteria:**

- Subjects treated at the Instituto de Investigaciones Médico-Biológicas de la Universidad Veracruzana, diagnosed with fatty liver.
- Willingness to voluntarily participate in the study and signing of informed consent.
- Age over 18 years, both sexes.
- Patients with evidence of hepatic steatosis and overweight or obesity.
- Patients with evidence of hepatic steatosis, diabetes mellitus, and overweight or obesity.
- Patients with evidence of steatosis plus metabolic risk abnormalities (waist circumference >102 cm in men, 88 cm in women, blood pressure >130/85 mmHg or on specific treatment, triglycerides >150 mg/dL or on specific treatment, HDL cholesterol <40 mg/dL in men, <50 mg/dL in women or on specific treatment, HOMA-IR >2.5, CRP >2 mg/dL, or prediabetes defined by fasting plasma glucose 100-125 mg/dL, 2-hour postload glucose 140-199 mg/dL, or HbA1c between 5.7% and 6.4%).
- Agree not to start a diet program during the study.
- Agree not to change their current exercise plan during the study.

### **Exclusion criteria:**

- Patients who meet diagnostic criteria for MAFLD with normal weight.
- Patients with terminal illness, cancer, or end-stage renal disease on renal replacement therapy.
- Pregnant women.
- Patients who are unable to understand or follow the study protocol.
- Sensitivity to the components of the formula.

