**Elimination criteria:**

- Patients who do not comply with the follow-up time and drug administration.
- Patients who do not comply with proper drug intake.
- Patients with intolerance or severe adverse effects to the components of the drug.
- Patients who are unable to undergo FibroScan® examination due to technical limitations.

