#### **4. Follow-up and surveillance**

1. Physical activity: It will be evaluated by means of the international physical activity questionnaire (IPAQ) that categorizes the levels of physical activity in: low (category 1), moderate (category 2) and high (category 3) according to the intensity, frequency and duration of the training. The recommendation will be made not to modify the usual training plan.
2. Nutritional plan: The monitoring will be carried out in a personalized way through a monthly face-to-face nutritional consultation.
3. Pharmacological treatment: The adherence to the pharmacological treatment will be monitored through a monthly telephone interview. Telephone assistance will be available to resolve doubts and report adverse effects.

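### Nothing stops or records use of non-study alpha-lipoic acid or milk thistle, so use in the placebo arm may dilute the product-versus-placebo contrast

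*Protocol*

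**What the plan says.** The overall objective compares the combination product plus diet with "placebo plus a Mediterranean diet on fibrosis and steatosis in patients with MAFLD after 24 weeks of treatment". The specific objectives apply the same contrast to stiffness, CAP and laboratory measures at 12 and 24 weeks. With both arms on the diet, exposure to the two compounds is what separates them.

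The rules that could protect that separation are these:

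- **Exclusion criteria.** The compounds appear once, as "Sensitivity to the components of the formula". Prior or current use is not mentioned and no washout is set.
- **Inclusion criteria.** Two undertakings on outside behaviour are required: "Agree not to start a diet program during the study" and "Agree not to change their current exercise plan during the study". Neither concerns the compounds under test.
- **Elimination criteria.** These cover follow-up, tolerance, FibroScan feasibility and the study drug, for example "Patients who do not comply with proper drug intake". Non-study use of the same actives is not covered.
- **Follow-up and surveillance.** Physical activity, the nutritional plan and study treatment are followed. For treatment, "The adherence to the pharmacological treatment will be monitored through a monthly telephone interview". No question about other products is stated.
- **Initial assessment.** A complete medical history is taken, but no rule acts on what it finds about supplements.

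**The concern.** A patient already taking milk thistle or alpha-lipoic acid meets every entry rule, can be allocated to placebo and can go on taking it. A placebo patient can also start during the 24 weeks. Either way, part of the placebo arm is exposed to what is being tested, and the difference between arms is pulled towards zero.

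Eligibility and concomitant-product rules are protocol content, so a separate analysis plan would not normally supply them. An analysis plan also could not recover the information afterwards, because no step collects it. If the trial showed no difference, nobody could say whether off-study use had contributed.

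The protocol gives some reason to think of such use. It recruits "Patients regularly attending the outpatient clinic of the Gastroenterology Department" who already have the diagnosis, states that no drug is approved for the condition, and calls the intervention supplementation. This makes use conceivable but does not show how common it is.

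**Working it through.** **Inputs from the protocol.** Response of 70% versus 15% in ultrasound-graded steatosis, 80% power and 20 patients per arm before losses (Sample size calculation); 1:1 allocation (Interventions); significance at 0.05 (Analysis of the results), taken as two-sided because sidedness is not stated. The protocol gives no effect size or standard deviation for CAP or kPa, so the ultrasound rates are the only ones available for an illustration.

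**The plan's own figure.** With 70% versus 15%, two-sided 5% and 80% power, the pooled-variance formula is

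n = [1.96·√(2 × 0.425 × 0.575) + 0.842·√(0.70 × 0.30 + 0.15 × 0.85)]² / 0.55² = (1.370 + 0.489)² / 0.3025 ≈ 11.4.

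That is 12 per arm, or 15 with continuity correction. The stated 20 is not reproduced. That is a separate matter; 20 per arm is used below because it is what the protocol plans. At 20 per arm the power with no off-study use is 97% by normal approximation and 93% by exact Fisher.

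**Assumptions.** A share p of placebo patients take off-study product and respond as the active arm does. The active arm stays at 70%. Then

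placebo rate = 0.15 × (1 − p) + 0.70 × p = 0.15 + 0.55p

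difference = 0.70 − (0.15 + 0.55p) = 0.55 × (1 − p).

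**Results at 20 per arm, two-sided 5%.**

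| Placebo-arm use p | Users of 20 | Placebo rate | Difference (points) | Power, normal approx. | Power, exact Fisher |
|---|---|---|---|---|---|
| 0% | 0 | 15.0% | 55.0 | 97% | 93% |
| 10% | 2 | 20.5% | 49.5 | 91% | 84% |
| 20% | 4 | 26.0% | 44.0 | 82% | 71% |
| 30% | 6 | 31.5% | 38.5 | 70% | 56% |
| 50% | 10 | 42.5% | 27.5 | 41% | 29% |

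The difference reaches zero only at p = 100%.

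**If off-study product works less well.** Let it deliver a fraction e of the study product's effect. The difference becomes 0.55 × (1 − p × e). With p = 20% and e = 0.5 this is 0.55 × 0.90 = 49.5 points, which is the 10% row: Fisher power 84% instead of 71%. The table is therefore an upper bound on dilution, provided off-study product works no better than the study product.

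**The case against.** The strongest reply is that the protocol contains no evidence of such use in this population. That stands. The Background sentence on milk thistle, "It has been used in traditional Chinese medicine for the treatment of liver and biliary diseases", concerns another setting and says nothing about patients at this clinic. The 10 to 20% is an assumption shown as a range, not an estimate.

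Equal efficacy is also generous. The Background itself reports that alpha-lipoic acid given alone left histology and biochemical markers unchanged, and the planning rates come from a multi-component product added to metformin. This stands too, and is why the figures are a bound.

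The medical history at entry and the monthly nutritional visits and calls are occasions on which use might come to light. They weaken any suggestion that use would certainly go unnoticed. They do not close the gap, since no rule tells staff to ask, to record the answer or to act on it.

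Three stronger readings are tempting, and the documents support none of them:

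- *The contrast could be erased.* Only if every placebo patient took product that works as well as the study product. Partial use dilutes.
- *Prior use biases the baseline.* Randomisation balances prior use on average, though chance imbalance is possible with 40 to 50 patients. To say that continuing users contribute no contrast needs a ceiling, with study product adding nothing to existing use, and no section supports that.
- *The protocol freezes diet and exercise and overlooked only supplements.* Both arms start a new 1400 to 1700 kcal Mediterranean diet, so diet is not frozen. The undertaking about diet programmes itself fits awkwardly with that design.

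**Conclusion.** The gap is real and no other section closes it: non-study use of the two compounds is not excluded at entry, not restrained during treatment and not recorded. The consequence is possible dilution of the product-versus-placebo comparison, of unknown size. Under the worst-case assumption of equal efficacy, two to four users among 20 placebo patients shrink the expected difference by 10 to 20%. On the protocol's planning rates, four users take exact Fisher power below the intended 80%, while the normal approximation stays just above it at 82%.

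These figures rest on an assumed prevalence, assumed equal efficacy, an unaffected active arm and ultrasound response rates standing in for CAP and kPa. A reader might infer that a null result would be worthless. At these levels of use that does not follow; it would be harder to interpret because use was not recorded. The point is a cheap improvement.

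**What to change.** 1. In the exclusion criteria, add use of non-study alpha-lipoic acid or Silybum marianum products at, or within an interval set by the sponsor before, the baseline FibroScan. Excluding current use alone would admit someone who stopped the day before.
2. In the inclusion criteria, beside the exercise undertaking, add agreement not to take such products during the study.
3. At the existing monthly contacts (telephone interview and nutritional visit), ask about such use and record product and dates.
4. Keep every patient in the randomised arm for the main comparison, whatever use is reported. An analysis without those who report use may be shown as supportive only, because it conditions on behaviour after randomisation.

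Cost: two lines of eligibility wording, one question at contacts already planned, and a few screen failures.
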